10	STUDY MONITORING, AUDITING, AND INSPECTING	17
10.1	STUDY MONITORING PLAN.....	17
10.2	AUDITING AND INSPECTING	17
11	ETHICAL CONSIDERATIONS	17
12	STUDY FINANCES	17
12.1	FUNDING SOURCE.....	17
12.2	CONFLICT OF INTEREST	17
13	PUBLICATION PLAN	18
14	REFERENCES	18
15	APPENDICES (.....	18

List of Abbreviations

DTPA—Diethylene Triamine Penta-acetic Acid

Gd—Gadolinium

GBCA—Gadolinium Based Contrast Agent

MRI—Magnetic Resonance Imaging

Study Summary

Title	INVESTIGATOR-INITIATED INVESTIGATIONAL NEW DRUG (IND) APPLICATION TO STUDY THE EFFECTS OF INTRAVENOUSLY ADMINISTERED CA-DTPA AND ZN-DTPA TO TREAT PATIENTS WITH GADOLINIUM DEPOSITION DISEASE
Short Title	Ca/Zn DTPA for GDD
Protocol Number	GDD-001
Phase	Feasibility study
Methodology	Open label, non-randomization
Study Duration	1 year
Study Center(s)	Single center
Objectives	To see an increase in the elimination of Gd as measured by analysis of 24 hour urine collections.
Number of Subjects	20
Diagnosis and Main Inclusion Criteria	Gadolinium Deposition Disease (GDD)— *Symptoms of pain, depressed levels of consciousness, and skin induration post administration of a GBCA as well as elevated levels of gadolinium in 24 hr urine, greater than 30 days post administration of a GBCA
Study Product, Dose, Route, Regimen	Ca –DTPA (0.5 gm) administered IV push over 1 minute at the beginning of infusion, along with normal saline (over a 90 minute period), ending with another 0.5 gm DTPA dose with 10 minutes left of saline infusion. This will be followed the next day with Zn-DTPA (0.5 gm) administered IV push over 1 minute with normal saline (over a 90 minute period), ending with another 0.5 gm DTPA dose with 10 minutes left of saline infusion. A total of 1 gm of DTPA is administered at each treatment. This sequence will be administered 3 times, approximately 1 month apart.
Duration of administration	3 months
Reference therapy	No treatments established for this condition
Statistical Methodology	R, a language and environment for statistical computing (R Core Team, Vienna, Austria), will be used for all statistical computing. Statistical significance will be defined as p value less than 0.05.

1 Introduction

[figure not shown]
This document is a clinical research protocol and the described study will be conducted in compliance with the protocol, Good Clinical Practices standards and associated Federal regulations, and all applicable University research requirements. This study involves the treatment of patients with Gadolinium Deposition Disease (GDD) by intravenous administration of the chelating agents Ca-DTPA and Zn-DTPA. These chelating agents are approved for the treatment of individuals who have been contaminated by the actinide elements Plutonium (Pu), Americium (Am) and Curium (Cm). Based on the similarity of Gadolinium (Gd) to these elements and the use of DTPA as a chelate in Gd-based contrast agents (GBCAs) used in Magnetic Resonance Imaging (MRI), it is expected that Ca-DTPA and Zn-DTPA will be effective in reducing the total body burden of Gd in patients suffering from GDD.

1.1 Background

Gadolinium (Gd) is a heavy metal that is a principal component of many MRI contrast agents. Gd is always administered as a chelate in which the chelating agent (ligand) is expected to tightly bind the Gd ions. The Gd-chelate prevent the toxic Gd ions from directly interacting with cells and tissues. They also help to promote rapid elimination of the contrast agent from the body after the imaging procedure is complete. There are several commercially available Gd-based contrast agents (GBCAs). There have been growing concerns about the in vivo stability of some of these chelators. Nephrogenic Systemic Fibrosis (NSF) was first described in 2007 and was directly attributed to the release of Gd ions from MRI contrast agents, OptiMARK and Omniscan in particular, in patients with renal failure. More recently, patients with normal renal function have been reporting serious illnesses after administration of all classes of GBCAs.

1.2 Investigational Agent

[figure not shown]
Ca-DTPA (Pentetate calcium trisodium injection) and Zn-DTPA (Pentetate zinc trisodium injection) are FDA-approved products for removal of the radioactive actinides americium (Am), curium (Cm) and plutonium (Pu) for use in a radiological disaster or following nuclear terrorism event. Their mechanism of action is to chelate (bind) heavy metals in the circulation and enhance their renal elimination.

Pentetate calcium trisodium injection contains the sodium salt of calcium diethylenetriaminepentaacetate. Pentetate calcium trisodium is also known as trisodium calcium diethylenetriaminepentaacetate and is commonly referred to as Ca-DTPA. It has a molecular formula of $\text{Na}_3\text{CaC}_{14}\text{H}_{18}\text{N}_3\text{O}_{10}$ and a molecular weight of 497.4 Daltons. Ca-DTPA is supplied as a clear, colorless, hyperosmolar (1260 mOsmol/kg) solution in a colorless ampoule containing 5 mL. The ampoule contents are sterile, non-pyrogenic and suitable for intravenous administration. Each mL of solution contains the equivalent of 200 mg pentetate

calcium trisodium (obtained from 158.17 mg pentetic acid, 40.24 mg calcium carbonate and NaOH) in Water for Injection, USP. The pH of the solution is adjusted with NaOH and is between 7.3 - 8.3.

Pentetate zinc trisodium injection contains the sodium salt of zinc diethylenetriaminepentaacetate. Pentetate zinc trisodium is also known as trisodium zinc diethylenetriaminepentaacetate and is commonly referred to as Zn-DTPA. It has a molecular formula of $\text{Na}_3\text{ZnC}_{14}\text{H}_{18}\text{N}_3\text{O}_{10}$ and a molecular weight of 522.7 Daltons. Zn-DTPA is supplied as a clear, colorless, hyperosmolar (1260 mOsmol/kg) solution in a colorless ampoule containing 5 mL. The ampoule contents are sterile, non-pyrogenic and suitable for intravenous administration. Each mL of solution contains the equivalent of 200 mg pentetate zinc trisodium (obtained from 150.51 mg pentetic acid, 31.14 mg zinc oxide and NaOH) and water for injection, USP. The pH of the solution is adjusted with NaOH and is between 6.5 – 7.5.

Ca-DTPA and Zn-DTPA form stable chelates with metal ions by exchanging calcium or zinc for a metal of greater binding capacity. The radioactive chelates are then excreted by glomerular filtration into the urine

1.3 Preclinical Data

The log of thermodynamic binding constant (log K) of DTPA for Gd is comparable to those of the three heavy metals for which Ca-DTPA and Zn-DTPA are approved and far greater than the two most relevant physiological metals (Ca and Zn):

	Log K
Am	22.92
Cm	22.99
Pu ³⁺	20.58
Gd	22.46
Ca	10.74
Zn	18.75

Note that these are log binding constants; thus, Gd binds to DTPA as tightly as the approved metals (Am, Cm and Pu) and 4-12 orders of magnitude greater than Zn and Ca.

1.4 Clinical Data to Date

Prior to formal approval by the FDA in 2005, Ca-DTPA and Zn-DTPA had been used to treat contaminated workers in the nuclear energy industry. In the period from 1958 to 1987, 485 patients received a total of 3077 doses of DTPA, about two-thirds as the calcium salt. Minor transient effects were observed in 12 patients, but no serious or long-term effects were reported. One worker was administered a total of 583 g of DTPA, primarily as the zinc salt, over a 4-year period without any observed toxicological effects (the usual recommended human dosage for a single administration is 0.5 to 1 gram).

In France, over 500 workers have been given a single dose of these agents by slow intravenous infusion and over 200 workers have received multiple dosages without adverse effects.

One of the most widely used GBCA, Magnevist, is actually a chelate of Gd and DTPA. It is estimated that 80 million doses Magnevist have been administered to patients undergoing an MRI procedure, and it has exhibited a very high safety profile. Of note, 50 million doses of Omniscan, which employs a di-amide chelator, have been administered to patients. This agent incorporates 5% free ligand in order to improve safety as it serves to scavenge Gd ions released from its chelated form. A similar di-amide Gd chelate, Optimark, contains 10% free ligand for the same reason.

DTPA is also used as a chelator for radiopharmaceuticals employing other heavy metals, e.g., ^{99m}Tc -DTPA (TechneScan®DTPA) and ^{111}In -DTPA (Pentetate Indium Disodium In 111®) used as diagnostic agents in nuclear medicine. These agents have been safely used in millions of patients over the past four decades.

1.5 Dose Rationale and Risk/Benefits

The doses selected (1 gram each of Ca-DTPA and Zn-DTPA) are based on information in the package insert of these products for use as radionuclide decorporation agents.

It is worth emphasizing that DTPA (and other chelators in different GBCA products) represents the component that makes MRI contrast agents 'safe', and we will administer it in approximately 1/4 the standard dose of the MR contrast agents. As a side note, it should be observed that the total amount of DTPA ligand is approximately the same amount of free ligand that is delivered when a magnetic resonance angiogram is performed using Optimark as the contrast agent. Thus, the precedent exists for this in clinical practice, with the comparable intention of scavenging free Gd to minimize the potential for deposition.

2 Study Objectives

Primary Objective:

- To observe an increase in the elimination of Gd as measured by analysis of 24-hour urine collections.

Secondary Objective:

- To observe a measurable reduction or elimination of symptoms caused by administration of a GBCA.
- Evaluate chemokine mediators and function of the mononuclear phagocyte system prior to and after treatment with DTPA.

3 Study Design

3.1 General Design

This is an open-label study. Patients will be evaluated at a baseline visit to determine eligibility and obtain informed consent before proceeding on to study-related procedures. Most patients coming for treatment will have had prior gadolinium testing greater than 30 days post MRI/contrast agent that shows an elevated result, thus eligibility for chelation therapy.

In addition to previous gadolinium testing, subjects will be instructed to perform a 24-hour urine collection (at visit 0) to determine a baseline for evaluating the elimination of gadolinium before initiating the first treatment.

At the first and subsequent chelation therapy visits, a baseline blood pressure will be obtained, an IV will be placed by Vascular Interventional Radiology (VIR) nursing staff, and 1L of normal saline will be connected. Initially, 2.5 mL of Ca-DTPA (1 g/5 mL) will be administered over a period of 1 minute. Five (5)

minutes post DTPA blood pressure will be collected again. The saline will then be administered at a rate of 300 mL/hr over 30 minutes with the patient seated and with hands lowered by their sides to allow the chelator to dwell slightly in the soft tissues of the hands and feet. The patient will then be positioned in a supine position on a hospital bed/gurney and the infusion rate will then be increased to 750 mL/hr over the next 60 minutes. With 10 minutes remaining (80 minutes after the start of infusion), the remaining 2.5 mL of Ca-DTPA will be administered I.V. over a period of 1 minute. The infusion of saline will continue another 9 minutes, and the I.V. line will then be removed. The patient will be instructed to drink plenty of fluids that evening. The following day, the treatment will be repeated using Zn-DTPA.

The patient will be instructed to collect 24-hour total urine samples beginning once chelation therapy starts, and bring back to the lab the following days.

The process will be repeated monthly, for a total of 3 chelation treatment time-points.

Patients will come to clinic for follow up to be assessed for adverse events one week following each treatment. Patients will be asked to fill out pain/QOL questionnaires and given a brief physical exam. Patients who live greater than 3 hours away will be assessed via phone call and instructed to get labs drawn locally. Patients may be advised to seek medical attention if the investigator feels any adverse reaction is not expected or is severe.

The number and function of monocytes and macrophages will be evaluated using 6 mL of blood. A 6 mL blood sample will be obtained in a heparin (green-top) tube and used to determine of the number and function of monocytes and macrophages via flow cytometry (phagocytosis and respiratory burst). This sample will be kept at ambient temperature, and must be processed within 39 hours. These assays will be performed in accordance with the standard operating procedures in [name] laboratory and the UNC Flow Cytometry Core Facility.

Mediators of the MPS, including cytokines/chemokines, will be measured with a 6 mL blood sample obtained in a heparin (green-top) tube. Blood will be processed to plasma by centrifugation at 1500 x g for 5 minutes at 4°C. Plasma should be removed using a pipet and distributed evenly between two screw-top tubes. Plasma should be processed within 2 hours and stored at -80C until evaluation in accordance with standard operating procedures within [name] laboratory.

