6.3 **Visit 2-** The patient subject will come for the second infusion therapy with Zn-DTPA. Patient will void and have a baseline blood pressure taken prior to initiation of therapy. Blood samples will be collected by phlebotomy trained staff at the Clinical & Translational Research Center (CTRC) at UNC Memorial hospital. Patient blood samples will be obtained just prior to intravenous administration of Ca-DTPA or Zn-DTPA. IV placement will be done by nursing staff, normal saline infusion started, and Zn-DTPA injections will be done by investigator or one of the co-investigators exactly as the day prior. Five (5) minutes post injection of Zn-DTPA another blood pressure will be taken. Another 24-hour urine sample will be collected beginning after chelation therapy is initiated, to be returned then next day.

6.4 **Visit 3-** The patient will return to the hospital to drop off 24 hour urine for gadolinium testing, as well as a creatinine clearance. Blood chemistries calcium, zinc, magnesium and manganese will be evaluated, along with BUN, creatinine, sodium, potassium, chloride, phosphorus and CO₂.

6.5 **Visit 4-** The patient subject will come for a follow up assessment by a clinician 1 week (+5 days) following IV therapy, where pain and overall health assessments will be performed. If the patient lives more than 3 hours away, a phone-call follow up will be done and questionnaires will be supplied to be filled out and emailed prior to leaving the infusion therapy. The second therapy session will be scheduled for the following month.

6.6. **Visit 5-** Patient will return for 2nd round of infusion therapy to be done exactly as first, with day one of Ca-DTPA including pregnancy testing on women of child-bearing potential and pain scale assessment sheets for the week. Blood samples will be collected by phlebotomy trained staff at the Clinical & Translational Research Center (CTRC) at UNC Memorial hospital. Patient blood samples will be obtained just prior to intravenous administration of Ca-DTPA or Zn-DTPA.

6.7 **Visit 6-** Patient returns for day two of infusion therapy with Zn-DTPA. Blood samples will be collected by phlebotomy trained staff at the Clinical & Translational Research Center (CTRC) at UNC Memorial hospital. Patient blood samples will be obtained just prior to intravenous administration of Ca-DTPA or Zn-DTPA

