6.8 **Visit 7-** The patient will return to the hospital to drop off 24-hour urine for gadolinium testing, as well as a creatinine clearance. Blood chemistries calcium, zinc, magnesium and manganese will be evaluated, along with BUN, creatinine, sodium, potassium, chloride, phosphorus and CO₂.

6.9 **Visit 8-** One week post treatment follow up visit for health assessments as before. Third therapy session will be scheduled for one month out.

6.10 **Visit 9-** Patient returns for final round of infusion therapy to be done exactly as first two treatments with day one of Ca-DTPA, including pregnancy testing on women of child-bearing potential and pain assessment sheets for the week. Blood samples will be collected by phlebotomy trained staff at the Clinical & Translational Research Center (CTRC) at UNC Memorial hospital. Patient blood samples will be obtained just prior to intravenous administration of Ca-DTPA or Zn-DTPA

6.11 **Visit 10-** Patient returns for day two of infusion therapy with Zn-DTPA. Blood samples will be collected by phlebotomy trained staff at the Clinical & Translational Research Center (CTRC) at UNC Memorial hospital. Patient blood samples will be obtained just prior to intravenous administration of Ca-DTPA or Zn-DTPA

6.12 **Visit 11-** The patient will return to the hospital to drop off 24-hour urine for gadolinium testing, as well as a creatinine clearance. Blood chemistries calcium, zinc, magnesium and manganese will be evaluated, along with BUN, creatinine, sodium, potassium, chloride, phosphorus and CO₂.

6.13 **Visit 12-** Subject returns for final follow up assessments 1 week (+5 days) following last infusion therapy. If patient lives more than 3 hours away, a phone-call will be done by the treating physician or clinician.

6.14 **Visits 13-14-** Subjects will receive a phone call from the coordinator to go over pain the pain assessment scale at months 6 and 12 following treatment.

At any time in between treatments if the clinician or patient feels they need to be seen, they will be brought in to the clinic (or to their local healthcare provider) for evaluation and possible discontinuation of therapy.

7 Statistical Plan

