12.2 Conflict of Interest

Any investigator who has a conflict of interest with this study (patent ownership, royalties, or financial gain greater than the minimum allowable by their institution, etc.) must have the conflict reviewed by a properly constituted Conflict of Interest Committee with a Committee-sanctioned conflict management plan that has been reviewed and approved by the study sponsor prior to participation in this study. All University of UNC investigators will follow the University conflict of interest policy.

13 Publication Plan

Neither the complete nor any part of the results of the study carried out under this protocol, nor any of the information provided by the sponsor for the purposes of performing the study, will be published or passed on to any third party without the consent of the study sponsor. Any investigator involved with this study is obligated to provide the sponsor with complete test results and all data derived from the study.

14 References

1. Sieber MA1, Lengsfeld P, Walter J, Schirmer H, Frenzel T, Siegmund F, Weinmann HJ, Pietsch H., Gadolinium-based contrast agents and their potential role in the pathogenesis of nephrogenic systemic fibrosis: the role of excess ligand. *J Magn Reson Imaging*. 2008 May;27(5):955-62 doi: 10.1002/jmri.21368

15 Appendices

- A. Table of Events
- B. Visual Analog Pain Scale
- C. Quality of Life scale
- D. Copy of Consent Form

Time and Events Table:

	Pre-treatment Visit 0	V 1 Day 1	V 2 Day 2	V 3 Day 3	V 4 Day 7	V 5 Day 1 Mo 2	V 6 Day 2 Mo 2	V 7 Day 3 Mo 2	V 8 Day 7 Mo 2	V 9 Day 1 Mo 3	V10 Day 2 Mo 3	V 11 Day 3 Mo 3	V 12 Day 7 Mo 3	V 13-14 Mo 6 & 12
Physical Assessments	X				X				X				X	
Labs	X	X ^c		X		X ^c		X		X ^c		X		
24 hr urine gd	X	X ^a	X ^a			X ^a	X ^a			X ^a	X ^a			
Pain/QOL questionnaire	X				X ^e				X ^e				X ^e	X ^d
IV Ca-DTPA therapy		X				X				X				
IV Zn-DTPA therapy			X				X				X			

- a. Patients will begin 24hr urine collection immediately following therapy
- b. Assessments may be done by phone when patient lives greater than 3 hours away
- c. Urine pregnancy testing will be done on day one of therapy for WCBP

- d. Patients will be called to collect pain and QOL data at months 6 and 12
- e. Pain/QOL questionnaires will be filled out days 1-6 and returned day 7

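### Patients living more than 3 hours away can receive rounds 2 and 3 with no required physical exam since Visit 0, because the one-week exams at V4 and V8 become phone calls

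*Combined protocol and SAP*

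**What the plan says.** Section 6.1 includes a physical exam at Visit 0. For the follow-up one week after each treatment, Section 3.1 states: "Patients will be asked to fill out pain/QOL questionnaires and given a brief physical exam". For distant patients it goes on: "Patients who live greater than 3 hours away will be assessed via phone call and instructed to get labs drawn locally".

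Section 6 carries the rule through the visits:

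- **V4 (6.5):** "If the patient lives more than 3 hours away, a phone-call follow up will be done".
- **V8 (6.9):** "One week post treatment follow up visit for health assessments as before". The phone option is not written out here. It follows from the reference back to the previous visit and from Section 3.1, which covers the follow-up after every treatment.
- **V12 (6.13):** "If patient lives more than 3 hours away, a phone-call will be done by the treating physician or clinician".

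The Time and Events Table in Section 15 marks Physical Assessments at V0, V4, V8 and V12 only. Its footnote b reads "Assessments may be done by phone when patient lives greater than 3 hours away". In the text available for this review that footnote is not attached to a cell, so its exact scope is unclear, but the point does not depend on it.

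The later rounds repeat the first. Section 6.6 (V5) says "Patient will return for 2nd round of infusion therapy to be done exactly as first, with day one of Ca-DTPA including pregnancy testing", and Section 6.10 (V9) says "Patient returns for final round of infusion therapy to be done exactly as first two treatments with day one of Ca-DTPA".

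**The concern.** The protocol treats the physical exam as part of adverse event ascertainment. Section 3.1 places it in the follow-up whose purpose is to assess adverse events. Section 8.1 classes abnormalities found at screening as preexisting conditions, counts worsening of such a condition as an adverse event, and asks for new findings at the end of the study to be recorded. Each of these steps needs a later exam to set beside Visit 0. For a distant patient none is required, either before the next round or at the end.

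What is at stake is narrow: signs that can be seen or felt and that the patient does not mention, such as dermatitis or worsening induration or hyperpigmentation. They might not be seen before re-dosing, and they might be under-counted. Section 7.1 names the safety profile as a purpose of the 20 subjects, so the adverse event counts would pool patients examined to different degrees.

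**Working it through.** The plan gives no figure to reproduce. The check is to list every required exam, apply the distance rule, and see what remains before each re-dosing.

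1. **Required exams (Section 6; Time and Events Table).** V0, V4, V8, V12 = 4, of which 3 are after baseline.
2. **Apply the phone rule.** V4, V8 and V12 all become phone calls for a distant patient: 3 − 3 = 0 required post-baseline exams, against 3 for a near patient.
3. **Which of these precede a re-dosing?** V4 precedes round 2 (V5, V6) and V8 precedes round 3 (V9, V10). V12 follows the last infusion. Required exams between Visit 0 and the start of round 3 are therefore 2 for a near patient and 0 for a distant one.
4. **Is an exam required on a dosing day?** Section 6.2 lists voiding, blood pressure, a pregnancy test where applicable, blood samples, IV placement and, after the injection, a second blood pressure. It lists no exam, and V5 and V9 repeat that procedure. This is so for near and distant patients alike.
5. **Infusions affected.** All infusions: V1, V2, V5, V6, V9, V10 = 6. In rounds 2 and 3: V5, V6, V9, V10 = 4, so 4 of 6.
6. **Age of the last required exam.** Assume 30 days between rounds, so that V5 is day 31 counting V1 as day 1. Visit 0 is 0-7 days before V1.
   - Distant: at V5, 30 + (0 to 7) = 30-37 days; at V9, 60 + (0 to 7) = 60-67 days.
   - Near: V4 on day 7-12 (table day plus the 5-day window) gives 31 − 12 = 19 to 31 − 7 = 24 days. Counting one week from V2 instead (day 9-14) gives 17 to 22 days. Overall this is 17-24 days, and the same again at V9.

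| At the start of | Near patient | Distant patient |
|---|---|---|
| Round 2 (V5) | 17-24 days | 30-37 days |
| Round 3 (V9) | 17-24 days | 60-67 days |

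7. **Signs at issue.** Of the 8 qualifying symptoms in Section 4.1, 2 are visible signs (induration, hyperpigmentation). Of the 9 expected Ca-DTPA events in Section 8.1, 2 are visible (dermatitis, injection site reactions), or 3 if a skin allergic reaction is counted. Of the 3 for Zn-DTPA, none is. Section 8.1 also anticipates a flare of existing symptoms; that could involve the skin and is not in these counts.
8. **Patients affected.** Not stated; 0 to 20 of 20, each 1/20 = 5% of the sample.

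**The case against.** The strongest reply is that distant patients are closely watched anyway. They attend nine on-site visits after baseline (V1-V3, V5-V7, V9-V11). An investigator gives the injections in person at all six infusions. Section 8.2 makes questioning about adverse events mandatory at every contact, with examination where warranted. Section 6 allows an unscheduled evaluation in clinic or by a local provider, and Section 3.1 allows patients to be advised to seek care. Skin changes are usually noticeable to the person who has them, and Section 4.1 itself lists induration and hyperpigmentation among symptoms. The withdrawal rules in Section 8.4 turn on severe events and Grade 3 hypocalcemia, not on mild skin signs. Phone follow-up is also a reasonable, deliberate accommodation in a single-center feasibility study.

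Most of this stands, and it limits the point to signs nobody reports or suspects. It does not remove the point, because every exam it relies on is discretionary.

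Three stronger readings are tempting, and the documents do not support them:

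- **All three phone contacts bear on re-dosing.** Only V4 and V8 do. V12 comes after the last dose and affects only end-of-study recording.
- **Near patients are examined just before dosing and distant patients are not.** Nobody has a required exam on the V5 or V9 dosing day. The difference is the one-week exam.
- **Safety monitoring or the treatment effect is compromised.** Blood chemistries, including calcium, are scheduled on site at V3, V7 and V11 for everyone. The study has one arm, so no treatment contrast is biased.

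**Conclusion.** The gap is real but small. For patients more than 3 hours away, both required exams between Visit 0 and re-dosing are replaced by phone calls, and nothing on the dosing days takes their place. Rounds 2 and 3 can therefore be given with no required exam since Visit 0. Separately, the V12 phone call means the end-of-study comparison of exam findings described in Section 8.1 is not assured for these patients.

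The schedule facts come directly from the protocol, except that the phone option at V8 is read from Sections 3.1 and 6.9 together. The ages of the exams rest on the assumed 30-day interval. Neither the number of distant patients nor the number of signs that would be missed can be estimated from the documents, and nothing in them shows that a missed sign would change a re-dosing decision. This is an optional, inexpensive improvement, not a flaw in the study's conclusions.

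**What to change.** Amend Sections 6.6 and 6.10 and the Time and Events Table. Any subject whose preceding one-week contact was by phone has a brief targeted exam (skin, injection site, symptomatic areas), compared with the Visit 0 findings, before infusion at V5 and V9. State in the safety report that distant patients' follow-up after round 3 was by phone, so the end-of-study exam comparison in Section 8.1 is not available for them. Splitting adverse events by mode of contact is not worth adding: with at most 20 subjects it would tell the reader little.

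The cost is protocol and table wording plus a few minutes of investigator time at two existing visits. There are no new visits and no extra exams for near patients.

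What remains afterwards: distant patients have 2 required post-baseline exams against 3, so the difference falls from 3 − 0 = 3 to 3 − 2 = 1. Their exams come about 17-24 days later than a near patient's one-week exam, again on a 30-day interval, so they detect signs that persist and not those that have cleared. V12 stays a phone call.
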